7.2.3. Liver-Related Laboratory Evaluations

Liver-related abnormalities after initial study drug dosing will be examined and summarized using the number and percentage of participants who were reported to have the following laboratory test values for postbaseline measurements:

- Alanine aminotransferase (ALT): (a) $> 3 \times \text{ULN}$, (b) $> 5 \times \text{ULN}$, (c) $> 10 \times \text{ULN}$, (d) $> 20 \times \text{ULN}$
- Aspartate aminotransferase (AST): (a) $> 3 \times \text{ULN}$, (b) $> 5 \times \text{ULN}$, (c) $> 10 \times \text{ULN}$, (d) $> 20 \times \text{ULN}$
- ALT or AST: (a) $> 3 \times \text{ULN}$, (b) $> 5 \times \text{ULN}$, (c) $> 10 \times \text{ULN}$, (d) $> 20 \times \text{ULN}$
- Total bilirubin: (a) $> 1 \times \text{ULN}$, (b) $> 2 \times \text{ULN}$
- Alkaline phosphatase (ALP) $> 1.5 \times \text{ULN}$
- ALT or AST $> 3 \times \text{ULN}$ and total bilirubin: (a) $> 1.5 \times \text{ULN}$, (b) $> 2 \times \text{ULN}$
- ALT or AST $> 3 \times \text{ULN}$ and total bilirubin $> 2 \times \text{ULN}$ and ALP $< 2 \times \text{ULN}$

For individual laboratory tests, participants will be counted once based on the most severe postbaseline value. For both the composite endpoint of ALT or AST and total bilirubin, and the composite endpoint of ALT or AST, total bilirubin, and ALP, participants will be counted once when the criteria are met at the same postbaseline visit date. The denominator is the number of participants in the Safety Analysis Set with nonmissing postbaseline value of the tests in evaluation at the same postbaseline visit date.

Listings of liver-related laboratory tests will be provided.

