4.3. Exclusion Criteria

Participants who meet *any* of the following exclusion criteria at screening and randomization are not eligible to be enrolled in this study:

- 1) Received any investigational drug, RDV, or other antiviral treatment for COVID-19
- 2) ALT or AST $> 5 \times$ ULN
- 3) IMV, noninvasive mechanical ventilation, ECMO, or RRT for AKI
- 4) Positive serum pregnancy test at screening for women of childbearing potential or currently breastfeeding
- 5) Known hypersensitivity to the investigational drug, metabolites, or formulation SBECD

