7.2.2.1. Treatment-Emergent Laboratory Abnormalities

Treatment-emergent laboratory abnormalities are defined as values that increase at least 1 toxicity grade from baseline at any postbaseline time point, up to and including the date of last dose of study drug plus 30 days. If the relevant baseline laboratory value is missing, any abnormality of at least Grade 1 observed within the time frame specified above will be considered treatment emergent.

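### The liver table in SAP 7.2.3 ignores baseline, so persisting entry elevations dilute its > 3 x ULN, bilirubin, ALP and combined rows; showing these by baseline status is a cheap improvement

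*SAP*

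**What the plan says.** SAP 7.2.3 describes its purpose as follows: "Liver-related abnormalities after initial study drug dosing will be examined and summarized". The summary is the "number and percentage of participants who were reported to have the following laboratory test values for postbaseline measurements". The tiers are 3, 5, 10 and 20 x ULN for ALT, for AST and for either one; 1 and 2 x ULN for bilirubin; and 1.5 x ULN for ALP. Two kinds of combined criterion follow. One is ALT or AST > 3 x ULN with bilirubin above 1.5 or 2 x ULN. The other is ALT or AST > 3 x ULN with bilirubin > 2 x ULN and ALP < 2 x ULN.

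For single tests, "participants will be counted once based on the most severe postbaseline value". Combined criteria must be met on one postbaseline visit date. The denominator is the "number of participants in the Safety Analysis Set with nonmissing postbaseline value of the tests in evaluation", also on one visit date. Nothing in the section compares with baseline or separates participants who began above a threshold.

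Protocol 4.3, exclusion criterion 2, reads "ALT or AST $> 5 \times$ ULN" and applies to participants meeting "exclusion criteria at screening and randomization are not eligible to be enrolled". No exclusion criterion mentions bilirubin or ALP.

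SAP 7.2.2.1 takes a different approach. Treatment-emergent laboratory abnormalities are "values that increase at least 1 toxicity grade from baseline at any postbaseline time point", and Appendix 2 item 20 lists ALT, AST, ALP and total bilirubin among the tests covered.

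**The concern.** The permitted entry range overlaps the lowest transaminase tier. A participant who enters with AST at 4 x ULN and still has one postbaseline value above 3 x ULN is counted as having an abnormality after dosing, even if AST is falling. If bilirubin was also above 2 x ULN at entry and both persist on one visit date, the participant meets a combined criterion with neither component new.

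Hepatic toxicity was a named topic for the first DMC safety review (protocol 8.2.1.1), so readers will look at this table. Counts made up partly of entry elevations make the two arms look more alike in relative terms than the new-onset rates do. They also leave the reader unable to tell new combined-criterion cases from pre-existing ones without going through listings. The combined criteria matter most here, because no summary of them against baseline is planned anywhere in the SAP.

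**Working it through.** The plan states no figure for this table, so there is nothing to reproduce. The check is a comparison of the text, followed by an illustration.

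**Which rows are affected**

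- ALT, AST, or either > 3 x ULN: affected. Entry above 3 and up to 5 x ULN is allowed.
- The same tests > 5, > 10 and > 20 x ULN: not affected. An eligible participant enters at or below 5 x ULN and reaches these rows only by rising.
- Bilirubin and ALP rows: affected. There is no entry limit.
- Combined criteria: affected. All are built on ALT or AST > 3 x ULN plus bilirubin.

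**What covers baseline elsewhere**

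- SAP 7.2.2: a rise of at least one grade, one test at a time.
- SAP 7.2.1: baseline and change from baseline for selected tests.
- SAP 5.2: baseline ALT, but not AST or bilirubin.
- SAP 7.2 and 7.2.3: listings.

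None of these tabulates the combined criteria against baseline or is specified to count how many entered above 3 x ULN. DAIDS grade cut-offs are not given in the documents, so no mapping of grades to 3 x ULN was used.

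**Illustration for the > 3 x ULN row**

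All inputs are assumptions:

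- q = share entering above 3 x ULN
- s = share of those with a postbaseline value still above 3 x ULN, taken as equal in both arms
- r = new-onset rate among the rest: 6% RDV, 3% placebo (true ratio 2.00, true difference 3.0 points)

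Observed rate = q·s + (1 − q)·r. Observed difference = (1 − q)·(6% − 3%).

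For q = 1% and s = 50%, RDV is 0.005 + 0.99 × 0.06 = 6.44% and placebo is 0.005 + 0.99 × 0.03 = 3.47%. The ratio is 6.44/3.47 = 1.86.

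| q | s | RDV | Placebo | Ratio | Difference (points) | Pre-existing share of counted, RDV / placebo |
|---|---|---|---|---|---|---|
| 1% | 50% | 6.44% | 3.47% | 1.86 | 2.97 | 8% / 14% |
| 1% | 100% | 6.94% | 3.97% | 1.75 | 2.97 | 14% / 25% |
| 5% | 50% | 8.20% | 5.35% | 1.53 | 2.85 | 30% / 47% |
| 5% | 100% | 10.70% | 7.85% | 1.36 | 2.85 | 47% / 64% |
| 10% | 50% | 10.40% | 7.70% | 1.35 | 2.70 | 48% / 65% |
| 10% | 100% | 15.40% | 12.70% | 1.21 | 2.70 | 65% / 79% |

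Higher assumed onset rates (10% vs 5%) with s = 100% give 14.5% vs 9.75% at q = 5% (ratio 1.49, difference 4.75 points) and 19.0% vs 14.5% at q = 10% (ratio 1.31, difference 4.5 points). The true values are 2.0 and 5.0 points.

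**No drug effect:** with 5% new onset in both arms, q = 10% and s = 100%, both arms show 0.10 + 0.90 × 0.05 = 14.5%, ratio 1.00.

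**After a baseline split:** among participants at or below 3 x ULN at baseline, the rates return to 6% and 3%, ratio 2.00, on a denominator of (1 − q), that is 99% to 90% of participants.

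**The case against.** The strongest reply is that the table does what it says. It reports postbaseline values against absolute thresholds beside a concurrent randomized placebo arm, and it does not call them treatment-emergent or drug-related. Baseline is handled in SAP 7.2.2 for each single test, and the listings let a reader check any flagged case. Only numbers and percentages are planned, with no ratio or test, and the risk difference barely moves.

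Sampling error is also larger than the distortion. SAP 2.2 says enrollment stopped before 50% of plan, so below 558 participants, or at most about 372 and 186 under 2:1. At 6% vs 3% the standard error of the log ratio is √(0.94/22.32 + 0.97/5.58) = 0.465. A ratio of 2.0 would then have an approximate 95% interval of 2.0 ÷ 2.486 to 2.0 × 2.486, or 0.80 to 4.97, where 2.486 = exp(1.96 × 0.465).

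Most of this stands, and it is why the point is minor. What it does not answer is the combined criteria, which have no summary against baseline. Listings allow case-by-case reading but do not change the tabulated percentages.

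Stronger inferences are not supported:

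- *The safety plan ignores baseline.* SAP 7.2.2 shows otherwise.
- *The whole liver table is affected.* The three higher transaminase tiers are not, for eligible participants.
- *The rule creates a false drug signal.* With balanced baselines and no drug effect the ratio stays at 1.00.
- *Entry elevations add equal counts to the arms.* Under 2:1 randomization the arms share an expected percentage, not a count.

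**Conclusion.** The point holds as a minor matter of presentation and interpretability. In the > 3 x ULN, bilirubin, ALP and combined rows, persisting entry elevations raise the percentages in both arms and dilute the relative difference.

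The documents do not allow the size to be fixed. The range of 1.86 to 1.21 for a true ratio of 2.0 depends on the assumed prevalence, persistence and onset rates, on equal persistence in the arms, and on baseline balance. At 1% prevalence the dilution is modest. At 10% with full persistence, most counted participants in both arms would be pre-existing cases. The absolute difference is nearly preserved throughout. There is no contradiction between the protocol and the SAP, and no effect on the efficacy analyses.

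**What to change.** In SAP 7.2.3, keep the current counts and add one of two displays for the > 3 x ULN, bilirubin, ALP and combined rows:

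- each row by baseline status (at or below the threshold, already above it), each with its own denominator; or
- a shift table from baseline to worst postbaseline value.

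Name the participants at or below the threshold at baseline as the main comparison. State where participants with no baseline value go.

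For each combined-criterion case, show whether each component was already met at baseline and whether it worsened. Exclude no case. A rule that counted only cases with a newly met component would drop, for example, a participant who goes from AST 4 x and bilirubin 2.1 x ULN to 20 x and 8 x ULN, because both components were met at entry.

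The cost is SAP wording, a baseline condition in the program, extra table rows and a slightly smaller denominator for the main comparison. It needs no new data and no protocol amendment.

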7.3. Vital Signs and Respiratory Status

Descriptive statistics will be provided by treatment group for vital signs (including pulse rate, respiratory rate and blood pressure) as follows:

- Baseline value
- Values at each postbaseline visit
- Change from baseline at each postbaseline visit

A baseline value will be defined as the last available value collected on or prior to the date/time of first dose of study drug. Change from baseline to a postbaseline visit will be defined as the postbaseline value minus the baseline value.

In the case of multiple values in an analysis window, data will be selected for analysis as described in Section 3.8.3. No formal statistical testing is planned.

A by-participant listing of vital signs (including pulse rate, temperature, blood pressure, height, weight, and respiratory rate) and respiratory status (including SpO₂) will be provided by participant ID number and visit in chronological order.

7.4. Concomitant Medications

Medications collected at screening and during the study will be coded using the current version of the World Health Organization (WHO) Drug dictionary.

Concomitant medications are defined as medications taken while a participant took study drug. Use of concomitant medications will be summarized by preferred name using the number and percentage of participants for each treatment group. A participant reporting the same medication more than once will be counted only once when calculating the number and percentage of participants who received that medication. The summary will be ordered by preferred name in descending overall frequency. For drugs with the same frequency, sorting will be done alphabetically.

For the purposes of analysis, any medications with a start date prior to or on the first dosing date of study drug and continued to be taken after the first dosing date, or started after the first dosing date but prior to or on the last dosing date of study drug will be considered concomitant medications. Medications started and stopped on the same day as the first dosing date or the last dosing date of study drug will also be considered concomitant. Medications with a stop date prior to the date of first dosing date of study drug or a start date after the last dosing date of study drug will be excluded from the concomitant medication summary. If a partial stop date is entered, any medication with the month and year (if day is missing) or year (if day and month are missing) prior to the date of first study drug administration will be excluded from the concomitant medication summary. If a partial start date is entered, any medication with the month and year (if day is missing) or year (if day and month are missing) after the study drug stop date will be excluded from the concomitant medication summary. Medications with completely missing start and stop dates will be included in the concomitant medication summary, unless otherwise specified. Summaries will be based on the Safety Analysis Set. No formal statistical testing is planned.

7.5. Other Safety Measures

Renal replacement therapy during the study will be listed.

A data listing will be provided for participants experiencing pregnancy during the study.

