8.6. Safety Analysis

All safety data collected on or after first investigational drug dose date through 30 days after the date of the last investigational drug dose will be summarized by treatment group (according to the investigational drug received). Data for the pretreatment period and after the date of last investigational drug dose plus 30 days will be included in data listings.

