8.9. Sample Size

A total of approximately 1116 participants will be randomized in a 2:1 ratio to 2 groups (744 in the RDV group and 372 in the saline as placebo group). This sample size achieves approximately 85% power to detect a hazard ratio of 0.70 at a two-sided alpha level of 0.05. In the sample size calculation, it is assumed that the event rate in the saline as placebo group is 35%. The hazard ratio and event rate in the saline as placebo group are based on the most conservative estimates of the primary end point (composite of all-cause mortality or IMV) and key α -controlled secondary end point (all-cause mortality) through Day 29 among a subset of participants with eGFR < 60 mL/min in the Division of Microbiology and Infectious Diseases Protocol 20-0006 Adaptive COVID-19 Treatment Trial (ACTT)-1 (hazard ratio of 0.67 and placebo rate of 33%).

The sample size calculation was done using software EAST (Version 6.5, module for log-rank test given accrual duration [120 days] and study duration [149 days] and 1 interim analysis using the Lan-DeMets approach with O’Brien-Fleming type spending function).

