- a Focused medical history will include date of first symptoms, overall symptoms, exposure source, demographics, baseline characteristics, concomitant medications, kidney or other transplant history, and allergies. If available, up to 3 SCr values prior to COVID-19 illness (eg, within the previous 6 months) should be provided. Document COVID-19 vaccine status. (Note: It should be documented whether participant is fully or partially vaccinated, including any booster[s] received, if applicable.)
- b Positive as determined by PCR via 1 validated assay at a local laboratory, if not performed within the last 4 calendar days.
- c Includes heart rate, temperature, and blood pressure.
- d Respiratory status includes respiratory rate and oxygenation: see Sections 6.2.1, 6.2.2, and 6.4.
- e Pulmonary radiographic imaging may be performed within 72 hours, if not already available and if needed to satisfy eligibility criteria.
- f Ordinal scale to be performed twice on Day 1: prior to randomization (for baseline predose score) and the worst score on Day 1.
- g Serum pregnancy test will only be done for women of childbearing potential. Women < 54 years of age with amenorrhea of ≥ 12 months may also be considered postmenopausal if their follicle stimulating hormone (FSH) level is in the postmenopausal range > 40 IU/L and they are not using hormonal contraception or hormonal replacement therapy. Results from within 48 hours prior to screening are acceptable.
- h Chemistry: alkaline phosphatase, AST, ALT, total bilirubin, total protein, albumin, lactate dehydrogenase, creatine phosphokinase, bicarbonate, blood urea nitrogen, calcium, chloride, creatinine, glucose, lipase, magnesium, phosphorus, potassium, sodium, uric acid. Results from within 48 hours prior to screening are acceptable.
- i Hematology: complete blood count with differential, hemoglobin and/or hematocrit, platelets. Results from within 48 hours prior to screening are acceptable.
- j Coagulation performed by central lab: international normalized ratio, prothrombin time, activated partial thromboplastin time, D-dimer, fibrinogen. Results from within 48 hours prior to screening are acceptable.
- k RRT will be measured at screening through Day 29 or until discharge from inpatient hospitalization, as well as at the Day 60 phone follow-up.
- l Nasopharyngeal swab collection for virologic (SARS-CoV-2) testing for participants on Days 1, 3, 5, 7, 14, 21, and 29 or until discharge, whichever is earlier.

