6.2.1. Analysis of Secondary Efficacy Endpoints

The key α -controlled secondary endpoint of all-cause mortality through Day 29 will be analyzed in a similar manner to the primary endpoint.

Initiation of IMV through Day 29 and time to recovery through Day 29 will also be analyzed in a similar manner to the primary endpoint except that a competing risk analysis approach will be used with death as the competing risk.

For analysis on time to recovery through Day 29, two sets of analyses will be conducted:

(1) Time to recovery through Day 29, in which the first recovery without further worsening in the ordinal scale score (ie, a score of > 4) by Day 29 will be considered an event; (2) Time to recovery through Day 29, in which the first recovery (regardless of further worsening or not) will be considered an event.

The clinical status assessed by the 8-point ordinal scale at Day 15 and Day 29 will be analyzed using a proportional odds model including treatment as the independent variable. Two models will be explored; one with baseline score as a continuous covariate and one without baseline score as a covariate. The odds ratio and 95% CI will be provided. The percentage of participants in each category will be summarized by treatment group. The assumption of odds proportionality will be assessed using a score test and reported. Clinical status by study day and change from baseline up to Day 29 will also be summarized by treatment group.

For participants without ESKD at baseline, the number of RRT-free days will be calculated between date of first dose and Day 29. The number of RRT-free days will be calculated as the number of full days from Day 1 to Day 29 that the participant was alive and did not receive RRT. The number of RRT-free days will be summarized by treatment group, and compared between treatment groups using Wilcoxon rank sum test.

The proportion of participants with recovery through Day 29 will be summarized by treatment group, and compared between treatment groups using the CMH test stratified by randomization strata. Similar for time to recovery analysis, two sets of analyses will be conducted: (1) The proportion of participants with recovery through Day 29, in which recoveries without further worsening by Day 29 is considered; (2) The proportion of participants with recovery through Day 29, in which recoveries regardless of worsening status by Day 29 is considered.

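### The readable plan lists renal replacement therapy but gives no by-arm estimate of how many participants newly start it, and RRT-free days can mask an excess

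*SAP*

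**What the plan says.** SAP 7.5 gives RRT one sentence as a safety measure: "Renal replacement therapy during the study will be listed".

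The readable by-arm RRT analysis after baseline is in SAP 6.2.1, for participants without end-stage kidney disease (ESKD): "The number of RRT-free days will be calculated as the number of full days from Day 1 to Day 29 that the participant was alive". Days on RRT are left out of the count. The score is summarised by arm and compared with a Wilcoxon rank sum test. RRT at baseline is also tabulated (SAP 5.2).

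On data collection, Protocol Appendix 3, footnote k, states: "RRT will be measured at screening through Day 29 or until discharge from inpatient hospitalization, as well as at the Day 60 phone follow-up".

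By-arm safety summaries stop 30 days after the last dose. For other data, Protocol 8.6 says: "Data for the pretreatment period and after the date of last investigational drug dose plus 30 days will be included in data listings". Primary and secondary end points are evaluated through Day 29 (Protocol 3).

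Other kidney-related output is planned by arm: treatment-emergent adverse events by class and term (SAP 7.1.6), and graded creatinine increases (SAP 7.2.2.2 and Appendix 2, item 20). Renal adverse events as a group are listed only, whereas the hypersensitivity group is both summarised and listed (SAP 7.1.6).

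**The concern.** The dosing restriction that motivates this trial is renal: the excipient accumulates when kidney function is poor, and tubular injury was seen in nonclinical studies (Protocol 1.3). Participants on RRT for acute kidney injury are excluded (Protocol 4.3). RRT that starts after the first dose in someone without ESKD is therefore a new event that can be dated. A reader of the results will want to know how many participants in each arm started dialysis.

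The readable plan answers with a different quantity. RRT-free days mixes death, RRT and the length of RRT, and days between dialysis sessions count as RRT-free. If remdesivir lowers mortality, days gained alive can offset days lost to new dialysis, and the score can look neutral.

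The other tables do not supply the count. A procedure is not itself an adverse event under Protocol 7.1.1; only the condition behind it may be. SAP 7.2 recognises that RRT distorts creatinine, and its sensitivity analysis drops values from RRT start to three days after RRT ends. Creatinine is thus least informative in the participants who started dialysis.

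**Working it through.** **Sizes.** The plan randomises "744 in the RDV group and 372 in the saline as placebo group". Its power statement reproduces. With a placebo rate of 35% and hazard ratio 0.70, the remdesivir rate is 1 − 0.65^0.70 = 26.0%. Expected events are 372 × 0.35 + 744 × 0.260 ≈ 324. Power is Φ(√(324 × 2/9) × |ln 0.70| − 1.96) = Φ(1.07) ≈ 85.7%, against the stated 85%. The primary calculation is not in question; it only fixes the sizes.

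ESKD is capped at 20% of participants (Protocol 5.1.1), and enrolment stopped below 50% of 1116, that is below 558 (SAP 2.4). With the cap filled, 0.80 × 558 ≈ 446 participants, or about 297 v 149, is the ceiling without ESKD. At planned size the figure is 0.80 × 1116 ≈ 893, or about 595 v 298.

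**Why the score can mask an excess.** Assume for illustration that death and new RRT are independent. The share with the full 29 days is (1 − death) × (1 − new RRT). Each cell shows remdesivir v placebo.

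| New RRT | Deaths 25% v 25% | Deaths 20% v 25% |
|---|---|---|
| 20% v 10% | 0.600 v 0.675 | 0.640 v 0.675 |
| 10% v 5% | 0.675 v 0.7125 | 0.720 v 0.7125 |
| 6% v 3% | 0.705 v 0.7275 | 0.752 v 0.7275 |

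A five-point fall in mortality halves the visible gap in the first row and reverses it in the other two, although new RRT has doubled in each.

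**Simulation.** All event inputs are assumptions; the documents give no RRT rate for this population. Deaths are uniform on Days 3–29 and RRT starts uniformly on Days 2–15. RRT lasts 3–14 days (lower ends) or to death or Day 29 (upper ends). RRT-free days are compared by a two-sided Wilcoxon test at 0.05, and incidence by a pooled z-test. At about 297 v 149, the proportion of trials that detect the excess is:

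| New RRT | RRT-free days, equal deaths | Direct incidence | RRT-free days, deaths 20% v 25% |
|---|---|---|---|
| 20% v 10% | 26–41% | about 75–77% | 7–17% |
| 10% v 5% | 12–17% | 40–43% | 1–3% |
| 6% v 3% | about 7% | 23–27% | under 1% |

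Repeat runs move the entries by up to about three percentage points. At an assumed 160 v 80, the equal-deaths figures for 20% v 10% are about 15% and 47%. At planned size with 3–14-day RRT they are 51% and 97%; with deaths at 20% v 25% they are 13% and 98%.

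**A second set of inputs.** This borrows the protocol's reference placebo rate ("hazard ratio of 0.67 and placebo rate of 33"%) as the death rate, and the design hazard ratio of 0.70 for death. The remdesivir death rate is 1 − 0.67^0.70 = 24.4%. RRT runs from Days 2–14 to death or Day 29, daily or on three days in seven. At 298 v 149 with new RRT 20% v 10%, the score finds remdesivir worse in 40% (daily) or 20% (three in seven) with equal deaths, and in 4% or 1% with the mortality benefit.

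**What a direct estimate would give.** At 297 v 149 and 20% v 10%, the standard error is √(0.20 × 0.80/297 + 0.10 × 0.90/149) = 0.034. The difference is 10 points (95% CI about 3.4 to 16.6). For 10% v 5% it is 5 points (about 0.1 to 9.9).

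**Day 60.** With a last dose on Days 1–5, safety summaries end on Days 31–35. Days 36–60, 25 of the 60, fall outside even the longest window. No readable by-arm summary uses Day 60 RRT status.

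**The case against.** Four objections carry weight.

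*Redaction.* Exploratory end points are blacked out in both documents. SAP Appendix 2, item 17, defines peak creatinine through Day 29 in participants without ESKD, yet no readable end point uses it, so kidney items evidently sit in the redacted text. New RRT or Day 60 RRT may be among them. This stands: neither can be called missing from the plan.

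*The information is not lost.* Listings cover all randomised participants and show the randomised arm (SAP 3), so a reader could count by hand. Laboratory abnormalities that need intervention must be recorded as adverse events (Protocol 7.6), and the data monitoring committee's first meeting reviewed renal toxicity (SAP 2.2). A reader might infer that the trial cannot report how many started dialysis, or could show no kidney signal at all. The documents do not support either inference. The gap is a planned estimate with its uncertainty.

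*The direct comparison is also weak at low rates.* The nearest document figure is indirect. In the earlier trial, which did not include baseline eGFR below 30, stage 3 acute kidney injury (which includes starting RRT) occurred in 28/512 = 5.5% v 34/500 = 6.8% (Protocol 1.3). Near 6% v 3%, incidence would miss about three doublings in four. This stands and limits what the added table can claim.

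*Counting death is deliberate.* Days alive without RRT is a legitimate way to handle death. That is correct, and the score should stay; it answers a different question. New RRT also partly reflects the course of COVID-19, since ongoing acute kidney injury is admitted at entry. That is why it needs a randomised comparison rather than case-by-case reading.

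**Conclusion.** The point holds for the readable plan. RRT is only listed as a safety measure, and the one post-baseline by-arm RRT result can be offset by a mortality benefit. How much this matters depends on assumed rates. For 20% v 10% at about 297 v 149 with equal deaths, detection is 26–41% with RRT-free days and about 75–77% with direct incidence. It falls to 7–17% for the score if remdesivir also lowers death to 20% v 25%. At 10% v 5% and 6% v 3% both are lower, and smaller sizes reduce both further.

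The protocol sets no margin or formal test for kidney harm, so this is not a failed safety test. Nothing in the documents shows that remdesivir raises RRT. After the early stop, the value of the change lies in a clear estimate with an interval. It is a cheap improvement worth making, not a threat to the primary analysis. The Day 60 part is conditional on what the redacted sections contain.

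**What to change.** In SAP 7.5, for participants without ESKD at baseline, add by arm:

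1. The number and percentage starting RRT after the first dose through Day 29, the cumulative incidence with death as a competing event, and the between-arm difference with its 95% CI. Show this beside the RRT-free-days result.
2. If the redacted sections do not already provide it, Day 60 status: alive and RRT-free, alive on RRT, dead, or unknown.

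Keep the listing, and describe the new results as estimation.

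The cost is SAP wording and two tables from data already collected. SAP Appendix 2 already has rules for RRT at baseline and missing RRT end dates (item 10) and competing-risk code (item 26). The downsides are wide intervals after the early stop and some unknown Day 60 status, so the unknown count must be shown. No dose or treatment rule changes.
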